#### **9.1.5. Appropriateness of Assessments**

The clinical safety parameters in this study are routine elements of clinical health assessment and Phase 2 drug development. The disease activity and health outcome measurements are used both in clinical practice and psoriasis clinical trials. Psoriasis is associated with numerous skin based symptoms and HRQOL impairment, which justifies the use of psoriasis symptom severity as well as dermatologic and generic HRQOL assessments used in this study (Kimball et al. 2005; EMA 2004).

## 9.2. Adverse Events

Investigators are responsible for monitoring the safety of subjects who have entered this study and for alerting Lilly or its designee to any event that seems unusual, even if this event may be considered an unanticipated benefit to the subject.

The investigator is responsible for the appropriate medical care of subjects during the study.

Investigators must document their review of each laboratory safety report.

The investigator remains responsible for following, through an appropriate health care option, AEs that are serious or otherwise medically important, considered related to the investigational product or the study, or that caused the subject to discontinue the investigational product before completing the study. The subject should be followed until the event resolves, stabilizes with appropriate diagnostic evaluation, or is reasonably explained. The frequency of follow-up evaluations of the AE is left to the discretion of the investigator.

Lack of drug effect is not an AE in clinical studies, because the purpose of the clinical study is to establish treatment effect.

After the ICF is signed, study site personnel will record via eCRF the occurrence and nature of each subject's preexisting conditions, including clinically significant signs and symptoms of the disease under treatment in the study. In addition, site personnel will record any change in the condition(s) and any new conditions as AEs. Investigators should record their assessment of the potential relatedness of each AE to protocol procedure or investigational product via eCRF.

The investigator will interpret and document whether or not an AE has a reasonable possibility of being related to study treatment, study device, or a study procedure, taking into account the disease, concomitant treatment or pathologies.

A "reasonable possibility" means that there is a cause and effect relationship between the investigational product, study device, and/or study procedure and the AE.

The investigator answers yes/no when making this assessment.

Planned surgeries and nonsurgical interventions should not be reported as AEs unless the underlying medical condition has worsened during the course of the study.

If a subject's investigational product is discontinued as a result of an AE, study site personnel must report this to Lilly or its designee via eCRF, clarifying if possible, the circumstances leading to any dosage modifications, or discontinuations of treatment.

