### 9.2.1. Serious Adverse Events

An SAE is any AE from this study that results in any of the following outcomes:

- death
- initial or prolonged inpatient hospitalization
- a life-threatening experience (that is, immediate risk of dying)

- persistent or significant disability/incapacity
- congenital anomaly/birth defect
- important medical events that may not be immediately life-threatening or result in death or hospitalization, but may jeopardize the patient or may require intervention to prevent one of the other outcomes listed in the definition above. Examples of such medical events include allergic bronchospasm requiring intensive treatment in an emergency room or at home, blood dyscrasias, or convulsions that do not result in in-patient hospitalization, or the development of drug dependency or drug abuse.

Although all AEs occurring after signing the ICF are recorded in the eCRF, SAE reporting begins after the subject has signed the ICF and has received investigational product. However, if an SAE occurs after signing the ICF, but prior to receiving investigational product, it needs to be reported ONLY if it is considered reasonably possibly related to study procedure.

Study site personnel must alert Lilly or its designee of any SAE within 24 hours of investigator awareness of the event via a sponsor-approved method. If alerts are issued via telephone, they are to be immediately followed with official notification on study-specific SAE forms. This 24-hour notification requirement refers to the initial SAE information and all follow-up SAE information.

Pregnancy (during maternal or paternal exposure to investigational product) does not meet the definition of an AE. However, to fulfill regulatory requirements any pregnancy should be reported following the SAE process to collect data on the outcome for both mother and fetus.

Investigators are not obligated to actively seek AEs or SAEs in subjects once they have discontinued and/or completed the study (the subject summary eCRF has been completed). However, if the investigator learns of any SAE, including a death, at any time after a subject has been discharged from the study, and he/she considers the event reasonably possibly related to the study treatment or study participation, the investigator must promptly notify Lilly.

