#### **9.2.1.1. Suspected Unexpected Serious Adverse Reactions**

Suspected unexpected serious adverse reactions (SUSARs) are serious events that are not listed in the IB and that the investigator identifies as related to investigational product or procedure. United States 21 CFR 312.32 and European Union Clinical Trial Directive 2001/20/EC and the associated detailed guidances or national regulatory requirements in participating countries require the reporting of SUSARs. Lilly has procedures that will be followed for the recording and expedited reporting of SUSARs that are consistent with global regulations and the associated detailed guidances.

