**10.3.4. Safety Analyses**

Safety will be assessed by evaluating AE, laboratory analytes, vital signs, ECGs, and C-SSRS.

The induction period safety analyses will compare LY3074828 to placebo for which treatment group comparisons will be analyzed using the methods described in Section 10.3.1.1. The maintenance period safety analyses will summarize safety measures by treatment. Summaries of safety data collected during the follow-up period will be presented separately.

AEs will be coded according to the *Medical Dictionary for Regulatory Activities* and summarized by system organ class, preferred term, severity, and relationship to investigational product. A treatment-emergent adverse event (TEAE) is defined as an event that first occurred or worsened in severity after baseline. For each event classification term, the number of subjects experiencing a TEAE with that classification term will be tabulated.

Treatment-related TEAEs are defined as events that are indicated by the investigator on the eCRF to be related to treatment. If a subject reports the occurrence of a particular event more than once, the most severe of those events will be included in the summary tables of TEAEs, and the most severe of the most related of those events will be included in the summary tables of

treatment-related events. For events that are gender specific, the denominator and computation of the percentage will only include subjects from the given gender.

Additional safety parameters include laboratory analytes, vital signs, ECGs, and C-SSRS. Laboratory analytes and vital signs will be presented as mean changes from baseline and as incidence of abnormal values. ECG and C-SSRS data will be listed by subject. Other covariate data, including body weight, will be summarized by treatment group.

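### Protocol 9.2 defines a reasonable possibility of relatedness as an existing cause-and-effect relationship, which contradicts the lower threshold used elsewhere and lets possibly related events be answered no

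*Protocol*

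**What the plan says.** Protocol 9.2 contains four statements on relatedness:

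- What is recorded: "Investigators should record their assessment of the potential relatedness of each AE to protocol procedure or investigational product via eCRF".
- The question put to the investigator: "whether or not an AE has a reasonable possibility of being related to study treatment, study device, or a study procedure", judged in the light of the disease and of other treatments and pathologies.
- The definition: a reasonable possibility "means that there is a cause and effect relationship between the investigational product, study device, and/or study procedure and the AE".
- The form of the answer: "The investigator answers yes/no when making this assessment". There is no intermediate category.

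Other sections use the judgement or similar wording:

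- Protocol 10.3.4 defines treatment-related TEAEs as "events that are indicated by the investigator on the eCRF to be related to treatment". SAP 6.12.2 plans a table of them by system organ class and preferred term and adds no definition of relatedness.
- Protocol 9.2.1.1 defines SUSARs as "serious events that are not listed in the IB and that the investigator identifies as related to investigational product or procedure".
- Under Protocol 9.2.1, an SAE after consent but before dosing is covered by: "it needs to be reported ONLY if it is considered reasonably possibly related to study procedure". The same phrase, *reasonably possibly related*, governs SAEs that the investigator learns of after a subject has left the study.

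**The concern.** The definition sets a higher bar than the term it defines. A reasonable possibility is a threshold of suspicion; the existence of a causal relationship is a conclusion. With only yes or no available, an investigator who looks the term up and applies it as written can answer no for an event that might well be due to the drug. Another investigator, going by the ordinary meaning of the question, would answer yes for the same event.

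Two outputs are at stake. The treatment-related TEAE summaries would count fewer events than intended, and their content would depend partly on how each site read 9.2. The protocol's SUSAR definition, which turns on what the investigator identifies as related, would become narrower. The design adds some weight. Induction is double-blind with about 50 of 200 subjects on placebo, which makes it harder to assert that a cause exists in a single case. For maintenance, SAP 6.12 plans no safety comparisons, so attribution of individual events is not backed by a control rate.

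**Working it through.** No arithmetic applies: the plan gives no figure on this point, and none can be derived from it. The check is to set the wordings side by side and then follow the answer to where it is used.

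**Threshold implied by each wording**

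| Place | Wording | Threshold |
|---|---|---|
| Protocol 9.2, recording | potential relatedness | possible |
| Protocol 9.2, question | reasonable possibility | possible |
| Protocol 9.2, definition | "means that there is a cause and effect relationship between the investigational product, study device, and/or study procedure and the AE" | causation exists |
| Protocol 9.2.1, pre-dose SAE | reasonably possibly related | possible |
| Protocol 9.2.1, post-study SAE | reasonably possibly related | possible |

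Four wordings point to the lower threshold and one to the higher. The odd one out is the only explicit definition, and it is operative text in the current protocol, not an amendment-log entry.

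**Where the answer is used**

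1. *Treatment-related TEAE summaries.* Under Protocol 10.3.4, inclusion depends only on the investigator's eCRF entry, and SAP 6.12.2 tabulates on that basis. A no removes the event from these tables.
2. *SUSAR definition.* For an unlisted serious event, 9.2.1.1 makes the investigator's view of relatedness the deciding condition. No sponsor causality assessment appears in that definition.
3. *Pre-dose and post-study SAEs.* These rules state their own trigger in similar words and do not refer to the eCRF answer. They are affected only if a reader carries the 9.2 definition across.

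**Where the answer is not used**

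1. *On-study SAEs after dosing.* "Study site personnel must alert Lilly or its designee of any SAE within 24 hours of investigator awareness of the event", with no relatedness condition.
2. *Safety endpoint.* The Synopsis gives adverse event and discontinuation rates, whatever the cause.
3. *All-causality analyses.* These are the TEAE tables and the induction Fisher's exact test of pooled LY3074828 against placebo (SAP 6.12.2), the hypersensitivity and injection-site summaries (6.12.2.2, 6.12.2.3) and the SAE summaries (6.12.3). An event answered no stays in all of them.

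A side observation: for repeated events, 10.3.4 picks the most severe among the most related. With a yes/no answer, that ranking can only mean related before not related.

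**The case against.** A reader might infer from the definition that every event that is only possibly related must be answered no, and that such events then drop out of the treatment-related tables and SUSAR reporting. The documents do not support that.

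- Nothing instructs a no. The question itself still asks about a reasonable possibility, and the surrounding wording in 9.2 and 9.2.1 points the same way. The no follows only from a literal reading of one sentence.
- SUSARs are not shown to be lost. On-study SAEs after dosing reach the sponsor within 24 hours whatever the answer. Protocol 9.2 also asks investigators to alert the sponsor to anything unusual. Section 9.2.1.1 says that expedited reporting follows sponsor procedures consistent with global regulations.
- The secondary safety objective is barely touched, because its endpoint and the between-group test do not use relatedness.
- The blinding argument is partial. Placebo is given only in the 16-week induction, and in the 88-week maintenance period every regimen is LY3074828. How rarely an investigator could assert causation is a matter of opinion.
- The eCRF guidance may already use the lower threshold; it is not among the documents.

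All of this stands, and it limits the consequence. It does not remove the contradiction. The sponsor's procedures are outside the protocol, while the protocol's own SUSAR definition rests on the investigator. The treatment-related tables have no other source. The 24-hour rule for all SAEs does not cover pre-dose events, and the post-study rule carries its own relatedness condition.

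**Conclusion.** The sentence in Protocol 9.2 is wrong as written and should be corrected. It contradicts the term it defines and the other relatedness wording in 9.2 and 9.2.1. Applied literally, it can under-count the treatment-related TEAE summaries and narrow the investigator-based SUSAR definition. Applied unevenly, it makes the related-event counts differ by site for reasons unrelated to the drug. An effect on the pre-dose and post-study SAE triggers is possible but less direct.

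The size cannot be stated. The documents give no event rates and no indication of how many events would change class between the two readings, so any percentage would only restate an assumption. The conclusion assumes that at least some investigators apply the definition as printed and that no guidance outside these documents overrides it.

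**What to change.** Reconcile the passages by replacing the defining sentence in Protocol 9.2 with wording such as:

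> A reasonable possibility means that there are facts or arguments suggesting that the investigational product, device or procedure could have caused the AE; a cause-and-effect relationship need not be established.

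Use the same wording in the eCRF completion guidance, so that the yes/no field is answered to one threshold at all sites.

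The cost is one sentence in the protocol and one in the guidance. No endpoint, sample size or planned analysis changes. The downside is that related-event counts will be somewhat higher, which is the cautious direction for safety reporting.

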### 9.2.1. Serious Adverse Events

An SAE is any AE from this study that results in any of the following outcomes:

- death
- initial or prolonged inpatient hospitalization
- a life-threatening experience (that is, immediate risk of dying)

- persistent or significant disability/incapacity
- congenital anomaly/birth defect
- important medical events that may not be immediately life-threatening or result in death or hospitalization, but may jeopardize the patient or may require intervention to prevent one of the other outcomes listed in the definition above. Examples of such medical events include allergic bronchospasm requiring intensive treatment in an emergency room or at home, blood dyscrasias, or convulsions that do not result in in-patient hospitalization, or the development of drug dependency or drug abuse.

Although all AEs occurring after signing the ICF are recorded in the eCRF, SAE reporting begins after the subject has signed the ICF and has received investigational product. However, if an SAE occurs after signing the ICF, but prior to receiving investigational product, it needs to be reported ONLY if it is considered reasonably possibly related to study procedure.

Study site personnel must alert Lilly or its designee of any SAE within 24 hours of investigator awareness of the event via a sponsor-approved method. If alerts are issued via telephone, they are to be immediately followed with official notification on study-specific SAE forms. This 24-hour notification requirement refers to the initial SAE information and all follow-up SAE information.

Pregnancy (during maternal or paternal exposure to investigational product) does not meet the definition of an AE. However, to fulfill regulatory requirements any pregnancy should be reported following the SAE process to collect data on the outcome for both mother and fetus.

Investigators are not obligated to actively seek AEs or SAEs in subjects once they have discontinued and/or completed the study (the subject summary eCRF has been completed). However, if the investigator learns of any SAE, including a death, at any time after a subject has been discharged from the study, and he/she considers the event reasonably possibly related to the study treatment or study participation, the investigator must promptly notify Lilly.

#### **9.2.1.1. Suspected Unexpected Serious Adverse Reactions**

Suspected unexpected serious adverse reactions (SUSARs) are serious events that are not listed in the IB and that the investigator identifies as related to investigational product or procedure. United States 21 CFR 312.32 and European Union Clinical Trial Directive 2001/20/EC and the associated detailed guidances or national regulatory requirements in participating countries require the reporting of SUSARs. Lilly has procedures that will be followed for the recording and expedited reporting of SUSARs that are consistent with global regulations and the associated detailed guidances.

#### **9.2.1.2. Adverse Event Monitoring with a Systematic Questionnaire**

The C-SSRS (Posner et al. 2007; Columbia University Medical Center [WWW]) is a scale that captures the occurrence, severity, and frequency of suicide-related ideations and behaviors during the assessment period. The C-SSRS must be administered by appropriately trained site personnel. The tool was developed by the National Institute of Mental Health Treatment of

Adolescent Suicide Attempters trial group for the purpose of being a counterpart to the Columbia Classification Algorithm of Suicide Assessment (C-CASA) categorization of suicidal events. Subjects will be assessed according to the Schedule of Activities (Section 2).

CCI

### **9.2.2. Complaint Handling**

Lilly collects product complaints on investigational products and drug delivery systems used in clinical studies in order to ensure the safety of study participants, monitor quality, and to facilitate process and product improvements.

Subjects will be instructed to contact the investigator as soon as possible if he or she has a complaint or problem with the investigational product so that the situation can be assessed.

- Complaints must be reported by site staff within 24 hours of study/site personnel becoming aware of a product issue, regardless of the availability of the complaint sample.
- Retain the investigational product under appropriate storage conditions, if available or when obtained, until instructed to return it to Lilly.
- Product complaints for Non-Lilly Products (including concomitant drugs) that do not have a Lilly Product Batch or Control number are reported directly to the manufacturer per product label.
- Follow the instructions outlined in the Product Complaint Form for other reporting requirements.

### **9.3. Treatment of Overdose**

In case of suspected overdose, hematology, chemistry, vital signs, and oxygen saturation should be monitored and supportive care provided as necessary. There is no known antidote for LY3074828.

### **9.4. Safety**

#### **9.4.1. Electrocardiograms**

For each subject, ECGs should be collected according to the Schedule of Activities (Section 2). ECGs should be recorded according to the study specific recommendations included in the Schedule of Activities.

Any clinically significant findings from ECGs that result in a diagnosis and that occur after the subject receives the first dose of the investigational treatment should be reported to Lilly or its designee as an AE via eCRF.

### **9.4.2. Vital Signs**

For each subject, vital signs measurements should be conducted according to the Schedule of Activities (Section 2).

Any clinically significant findings from vital signs measurement that result in a diagnosis and that occur after the subject receives the first dose of study treatment should be reported to Lilly or its designee as an AE via eCRF.

### **9.4.3. Laboratory Tests**

For each subject, laboratory tests detailed in [Appendix 2](#) should be conducted according to the Schedule of Activities (Section 2).

Any clinically significant findings from laboratory tests that result in a diagnosis and that occur after the subject receives the first dose of investigational product should be reported to Lilly or its designee as an AE via eCRF.

### **9.4.4. Other Tests**

#### **9.4.4.1. Chest Radiography and Tuberculosis Testing**

Posterior-anterior view and lateral view (unless local standards dictate 1 view) chest radiography will be obtained at screening (Visit 1), unless the radiographs or medical report from chest radiography performed within 3 months before initial screening (per local standard of care for TB evaluation) are available to the investigator for review.

In addition, subjects will be tested as indicated in the Schedule of Activities (Section 2) for evidence of active or latent TB. A positive TB test result is indicated by a purified protein derivative (PPD) skin test response  $\geq 5$  mm induration documented approximately 48 to 72 hours after test application (regardless of Bacillus Calmette-Guerin vaccination history). In countries where the QuantiFERON-TB Gold test (or equivalent) is available and is preferred (in the judgment of the investigator) as an alternative to the PPD skin test for the evaluation of TB infection in a subject, that test may be used instead of the PPD test. If the QuantiFERON-TB Gold test is indeterminate, 1 retest is allowed. If the retest is indeterminate, then the subject is excluded from the study.

Subjects with documentation of negative TB test results within 3 months before initial screening may not need to repeat TB testing at screening (Visit 1) based on judgment of the investigator. Documentation of this previous test result must include a record of the size (in millimeters) of the induration response. A PPD test recorded as “negative” without documenting the size of induration (in millimeters) will not be acceptable and will require a retest.

However, subjects with a PPD skin test response  $\geq 5$  mm induration or a positive QuantiFERON-TB Gold test result at screening and no other evidence of active TB may be rescreened once and enrolled according to the following requirements:

- after receiving at least 4 weeks of appropriate ongoing prophylactic therapy for latent TB as per local standard of care

- no evidence of treatment hepatotoxicity (ALT and AST levels must remain  $\leq 2X$  ULN) upon retesting of serum ALT and AST levels before randomization

Such subjects must continue and complete appropriate latent TB therapy during the course of the study to remain eligible and must continue to meet all other inclusion and exclusion criteria for participation.

Subjects who have a documented history of completing an appropriate TB prophylaxis regimen with no history of reexposure since their treatments were completed and no evidence of active TB are eligible to participate in the study; these subjects should not undergo PPD or QuantiFERON-TB Gold (or other approved interferon-gamma release assay) testing.

Subjects who have had household contact with a person with active TB must be excluded unless appropriate and documented prophylaxis for TB has been given, as described above.

Subjects with any history of **active** TB are excluded from the study, regardless of previous or current TB treatments.

